8.11 WITHDRAWAL AND DISCONTINUATION

All subjects have the right to withdraw at any point during the study without prejudice. The investigator can discontinue any subject at any time at his/her discretion, or if continued participation in the study would result in harm to the subject. All efforts should be made by the investigator to retain the subject in the study. If a subject withdraws prematurely from the study, a genuine effort must be made to determine the

reason(s) the subject discontinued the study. The reason must be recorded in the subject's file and on the Study Exit Form.

8.12 SUBJECTS LOST TO FOLLOW-UP

Subjects who do not show up for a follow-up must be contacted to attempt to have them come for the follow-up. For those subjects who cannot be reached, every attempt to contact with the subject should be documented. If a subject misses two consecutive follow-up visits without any contact with the study staff, the subject will be considered lost-to-follow-up unless there is a further communication by the subject.

9 ADVERSE EVENTS (AEs)

Adverse Events are defined below. Adverse events that occur in the eye during the trial, whether they are considered to be device related or not, must be documented in the subject's records. Date of the event, its severity, treatment (if any) and the assessed relationship of the event to the study device will be recorded on the Adverse Event Form. Conditions which exist at the time the subject is enrolled will be considered pre-existing conditions and do not need to be recorded as adverse events unless they increase in severity during the study. Sites should document any known existing medical and ophthalmic conditions at the time of screening.

9.1 DEFINITIONS OF AE, SAE, SADE, USADE

Adverse Event	Any untoward medical occurrence in a subject who has been treated with the device that does not necessarily have causal relationship with the treatment.
Adverse Device Effect	Any unfavorable and unintended sign (including an abnormal laboratory finding), symptom, or disease that is possibly related to the study device.
Serious Adverse Event (SAE)	Any untoward medical occurrence that: 
• Results in death• Is life-threatening• Requires in-patient hospitalization or prolongs existing hospitalization• Necessitates medical or surgical intervention to preclude permanent impairment of a body function or permanent damage to a body structure• Sight-threatening
Unanticipated Adverse Device Effect	Any serious adverse effect on health or safety, any life-threatening problem or death caused by, or associated with a device if that effect, problem, or death was not previously

identified in nature, severity, or degree of incidence in the clinical investigational plan; or any other unanticipated serious problem associated with a device that relates to the rights, safety, or welfare of subjects (21 CFR 812.3(s)). Any sight-threatening event, whether listed in the protocol or not, is considered to be reportable as a UADE.

[figure not shown]
9.2 LIST OF ANTICIPATED POTENTIAL ADVERSE EVENTS

Anticipated potential adverse events listed below include those that might reasonably be expected to occur in this study because they are associated with glaucoma, ab-interno transluminal viscoelastic delivery, trabeculotomy, trabecular bypass stent, and/or the risk analysis for OMNI System. Adverse events may occur intra-operatively or post-operatively.

A 2D bar chart with 10 horizontal bars. The bars are black with white outlines. The heights of the bars decrease from left to right. The first bar is the tallest, followed by a shorter bar, then a group of three bars of intermediate height, then a group of three bars of intermediate height, and finally the shortest bar on the far right. The bars are set against a white background with black vertical grid lines.

²² To avoid double counting an event, events of IOP ≥ 10 mmHg above baseline IOP at ≥ 1 month visit that require management with systemic medication or secondary surgical intervention should be reported as “IOP increase requiring management with systemic medication at ≥ 1 month visit” or “Need for secondary surgery intervention to manage IOP,” respectively.

²³ Hypotony is defined as "early" if it occurs within 2 weeks of surgery and "late" if it occurs more than 2 weeks after surgery

9.3 REPORTING ADVERSE EVENTS AND UNANTICIPATED ADVERSE DEVICE EFFECTS

Identification, collection and reporting of adverse event information is the responsibility of the principal investigator. The investigator records the date of the event, its severity, treatment (if any) and the assessed relationship of the event to the study device on the Adverse Event Case Report Form (AE CRF).

Any ocular **serious adverse event** (SAE) should be reported to the study sponsor within one business day of learning of the event. Non-ocular SAEs should be reported to the study sponsor within two working days of learning of the event. Email the AE CRF to

[contact] and enter data in EDC system within two working days of learning of the event.

Any **unanticipated adverse device effects (UADE)** must be reported to the following two entities:

1. The study sponsor – Within one working day of the investigator first learning of the event, e-mail the AE CRF to [contact] and enter data in EDC; and
2. The reviewing IRB – As soon as possible, but no later than 10 working days after the investigator first learns of the event, report per the IRB's instructions.

The sponsor will conduct an evaluation of unanticipated adverse device effects. If the sponsor determines that an unanticipated adverse device effect presents an unreasonable risk to subjects, parts of the investigation presenting risks will be terminated. Termination will occur no later than 5 working days after the sponsor makes such a determination and no later than 15 working days after the sponsor first received notice of the effect.

10 STATISTICAL CONSIDERATIONS

10.1 SAMPLE SIZE CALCULATION

The sample size calculation is based on the primary effectiveness endpoint, mean change in unmedicated DIOP from baseline at the 12-month postoperative examination. The study goal is to determine, in reducing the IOP in eyes with OAG undergoing cataract extraction, either OMNI (ab-interno transluminal viscoelastic delivery AND trabeculotomy) is superior [REDACTED], or OMNI (ab-interno transluminal viscoelastic delivery alone) is not inferior to the [REDACTED] in lowering the IOP with a non-inferiority margin of 1.5 mmHg. Due to the multiplicity, the significance level is adjusted to a two-sided significance level of 0.025 for each of the two hypotheses. The statistical hypotheses for the primary effectiveness endpoint are as follows:

Hypothesis I:

$H_0: \mu_{02} = \mu_i$ versus $H_a: \mu_{02} < \mu_i$, where μ_{02} and μ_i are the mean change in unmedicated DIOP from baseline at the 12-month postoperative examination for the OMNI (ab-interno transluminal viscoelastic delivery AND trabeculotomy) and [REDACTED] groups, respectively. A negative mean change represents a mean reduction. The alternative hypothesis ($H_a: \mu_{02} < \mu_i$) is to prove that the mean change in unmedicated DIOP of the OMNI (ab-interno transluminal viscoelastic delivery AND trabeculotomy) group is lower than that of the iStent inject group. In other words, the OMNI (ab-interno transluminal viscoelastic delivery AND trabeculotomy) is superior to the [REDACTED] group in lowering the IOP.

Hypothesis II:

$H_0: \mu_{01} - \mu_i \leq -1.5 \text{ mmHg}$ versus $H_a: \mu_{01} - \mu_i > -1.5 \text{ mmHg}$, where μ_{01} and μ_i are the mean change in unmedicated DIOP from baseline at the 12-month postoperative examination for the OMNI (ab-interno transluminal viscoelastic delivery alone) and [REDACTED] respectively. Since negative μ_{01} and μ_i represent decreases in IOP, the alternative hypothesis ($H_a: \mu_{01} - \mu_i > -1.5 \text{ mmHg}$) is to prove that the mean change in unmedicated DIOP of the OMNI (ab-interno transluminal viscoelastic delivery alone) group is not worse than that of the [REDACTED] by 1.5 mmHg. In other words, the OMNI (ab-interno transluminal viscoelastic delivery alone) is not inferior to the [REDACTED] in lowering the IOP with a non-inferiority margin of 1.5 mmHg.

[REDACTED]

[REDACTED]

[REDACTED]

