10.4 EFFECTIVENESS ENDPOINTS AND ANALYSIS METHODS

Descriptive statistics on continuous variables will include mean, standard deviation, median, minimum, and maximum. Confidence intervals for change from baseline will be included for selected endpoints. Categorical variables will be summarized using frequency counts and percentages. Exact confidence intervals for point estimates may be provided. Statistical testing will be one-sided with a significance level of 0.025 or two-sided significance level of 0.05 unless specify otherwise. Data listings of individual subject data may be provided.

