10.4.1 PRIMARY EFFECTIVENESS ENDPOINT

The primary analysis of the primary effectiveness endpoint will be based on the AT population. The Baseline unmedicated DIOP will be used to impute the 12-month unmedicated DIOP for the subjects meeting any of the following criteria:

- Ocular hypotensive medications cannot be washed out properly at 12 months due to safety reasons.
- Have secondary surgical interventions (such as laser procedure or MIGS) to control IOP before the 12-month washout.
- Have any ocular procedures that can affect the IOP before the 12-month washout.

- Have IOP below 6 mmHg at 1 month or later
- Do not have the 12-month washed out DIOP due to any other reasons.

The change in unmedicated DIOP from baseline at 12 months will be calculated for each study eye as change = (12-month unmedicated DIOP – Baseline unmedicated DIOP).

The descriptive statistics (such as mean, standard deviation, median, minimum, and maximum) of the medication-free mean diurnal IOP and the change from baseline and the 95% confidence interval of the mean will be calculated for each of the three study groups. A two-sample t-test with a one-sided significance level of 0.025 will be used to compare the mean unmedicated DIOP change from baseline at 12 months for Hypotheses I and II described in Section [10.1](#). The two-sided 95% confidence interval based on the t-distribution will also be provided for the mean difference. In order to assess the pattern of the distribution, box-plots will be prepared for the medication-free mean diurnal IOP and its change from baseline for each of the three study groups.

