10.4.4 OTHER IMPORTANT CLINICAL EFFECTIVENESS OUTCOMES

The statistical analyses for the other effectiveness endpoints will be based on the available data of the AT population. The percent change in unmedicated DIOP from baseline at 12 months will be calculated for each study eye as

$$\% \text{ change} = \frac{(12\text{-month unmedicated DIOP} - \text{Baseline unmedicated DIOP})}{(\text{Baseline unmedicated DIOP})} \times 100\%.$$

The number and percent of subjects achieving $\geq 20\%$ reduction in unmedicated DIOP from baseline at 12 months (i.e., 12-month responder) will be calculated. The exact 95% confidence interval of the 12-month responder rate will be calculated by the binomial distribution for each study group separately. The difference in the 12-month responder between OMNI (transluminal viscoelastic delivery AND trabeculotomy) and [REDACTED] groups and the corresponding 95% confidence interval per normal distribution will be calculated. The same statistics will be provided for the difference in the 12-month responder between OMNI (transluminal viscoelastic delivery) and [REDACTED] groups. The same statistical methods will be used to summarize the subjects with an unmedicated DIOP between 6 and 18 mmHg inclusive at 12 months.

The descriptive statistics for the continuous variables will be used to summarize the change in number of ocular hypotensive medications used from screening to 12 months. The ANOVA with study treatment group (three groups) as the factor will be used to compare the mean difference in the change in number of ocular hypotensive medications used from screening to 12 months. The mean difference between OMNI (transluminal viscoelastic delivery AND trabeculotomy) and [REDACTED] and that between OMNI (transluminal viscoelastic delivery) and [REDACTED] will be evaluated using Dunnett's test. The same methods will be used to analyze the percent change in unmedicated DIOP from baseline to 12 months.

The analyses described in this section are exploratory in nature.

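### Section 10.1 splits alpha between the two primary hypotheses and section 10.4.1 does not; using Holm in both would reconcile them and add power for each hypothesis and for both

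*Combined protocol and SAP*

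**What the plan says.** Section 10.1 gives the study goal as an either/or. The first part is that "either OMNI (ab-interno transluminal viscoelastic delivery AND trabeculotomy) is superior" to the comparator (Hypothesis I). The second is that the viscoelastic-only arm is not inferior "in lowering the IOP with a non-inferiority margin of 1.5 mmHg" (Hypothesis II). On alpha it says: "Due to the multiplicity, the significance level is adjusted to a two-sided significance level of 0.025 for each of the two hypotheses". Each arm has one confirmatory test, and the 1.5 mmHg margin is stated only for the viscoelastic-only arm. Redacted blocks follow the hypotheses.

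Section 10.4.1, which specifies the primary analysis, says: "A two-sample t-test with a one-sided significance level of 0.025 will be used to compare the mean unmedicated DIOP change", and applies this to both hypotheses. It adds: "The two-sided 95% confidence interval based on the t-distribution will also be provided for the mean difference". This matches the general default in section 10.4: "Statistical testing will be one-sided with a significance level of 0.025 or two-sided significance level of 0.05 unless specify otherwise". Section 10.4.1 has no testing order, no recycling of alpha and no follow-on test.

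The other effectiveness endpoints (10.4.4 and 10.4.5) are labelled exploratory, so nothing else draws on the confirmatory alpha.

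**The concern.** Two things are unsettled. First, the level: 10.1 allots one-sided 0.0125 to each hypothesis, while 10.4.1 spends 0.025 on each. With either/or success, the second reading roughly doubles the chance of a false claim.

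Second, if the split in 10.1 governs, the visible method is one-step Bonferroni. After one hypothesis is rejected, its 0.0125 lapses. Holm would hand it to the other hypothesis at the same familywise error. Sections 1 and 2 list both comparisons as objectives, so power for each and for both is of interest even though one success meets the goal in 10.1.

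The combined arm can also earn only superiority. If it is better than the comparator by less than planned, the plan has no prespecified claim for it.

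**Working it through.** **Inputs.** From the documents: 459 randomized 1:1:1, 411 completers, about 10% dropout, margin 1.5 mmHg, and the two alpha statements. Assumed, because planned power, SD and effect are not visible: 70% to 90% power per test at one-sided 0.0125, or SD 3.5 to 5.0 mmHg with a combined-arm benefit of 1.0 to 1.5 mmHg and no true difference for the viscoelastic-only arm. Hypothesis II is taken in its evidently intended direction. With equal arms, equal variances and a shared control, the two test statistics have correlation 0.5.

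**The plan's own figure.** 411/3 = 137 per arm; 137/0.9 = 152.2, rounded up to 153; 3 × 153 = 459. This reproduces. The 411 cannot be rebuilt. For a 1.5 mmHg difference, SD = 1.5 / [√(2/137) × (z for alpha + z for power)]. At one-sided 0.0125 and 80% power this is 1.5 / [0.1208 × (2.241 + 0.842)] = 4.03, and at 90% power 3.52. At one-sided 0.025 it is 4.43 and 3.83. The rounder SDs suggest sizing at the split level, but that is inference.

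**Familywise error with both nulls true** (Φ₂ is the bivariate normal distribution function with correlation 0.5):
- 10.1, one-sided 0.0125 each: 1 − Φ₂(2.241, 2.241) = 0.023.
- 10.4.1, one-sided 0.025 each: 1 − Φ₂(1.960, 1.960) = 0.045 (upper bound 0.05).
- Holm: 0.023 with both nulls true, and at most 0.025 with one true.

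**Power at 80% per test.** Each statistic has mean 2.241 + 0.842 = 3.083.
- Both exceed 2.241: A = Φ₂(0.842, 0.842) = 0.687.
- A given one exceeds 2.241 and the other exceeds 1.960: B = Φ₂(0.842, 1.123) = 0.733.
- Bonferroni: each 0.800; both A = 0.687; at least one 2 × 0.800 − 0.687 = 0.913.
- Holm: each 0.800 + (B − A) = 0.846; both 2B − A = 0.778; at least one 2 × 0.846 − 0.778 = 0.913 (from unrounded values).

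| Power per test at 0.0125 | Each, Holm | Both, split to Holm | At least one, either method | Each, unsplit 0.025 |
|---|---|---|---|---|
| 70% | 75.3% | 55.7% to 66.3% | 84.3% | 79.0% |
| 80% | 84.6% | 68.7% to 77.8% | 91.3% | 86.9% |
| 90% | 93.1% | 83.2% to 89.4% | 96.8% | 94.1% |

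Simulation at 137 per arm over the assumed SDs and benefits, where the two tests need not have equal power, gives a gain from Holm of 3.0 to 9.8 points for Hypothesis I, 0.9 to 5.4 for Hypothesis II, 5.9 to 11.0 for both, and 0 for at least one.

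**Direction of Hypothesis II.** A negative change is a reduction. As written, the alternative is a difference (viscoelastic-only minus comparator) above −1.5, which a difference of +5 mmHg would satisfy. The null should be a difference of at least +1.5 and the alternative a difference below +1.5.

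**Optional combined-arm non-inferiority** (137 per arm, assumed SD 4.0; standard error 4.0 × 0.1208 = 0.483). At one-sided 0.0125:
- True benefit 1.0 mmHg: superiority Φ(1.0/0.483 − 2.241) = 43%; non-inferiority Φ(2.5/0.483 − 2.241) = 99.8%.
- True benefit 0.5 mmHg: 11% and 97%.

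For a 0.5 mmHg benefit over SD 3.5 to 5.0, superiority has 14% to 8%; non-inferiority with recycling has 99.5% to 87.6%. When Holm and this test were simulated together, familywise error did not exceed 0.025 in any null configuration tried.

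**The case against.** The strongest reply is that Bonferroni is valid and gives simple matching intervals, so nothing here is wrong. That stands: the gain is in efficiency.

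Several stronger readings are tempting and are not supported:
- A reader might infer that alpha is never recycled. Redacted text follows the hypotheses in 10.1 and could contain a testing order. Only the visible text, including an unredacted 10.4.1, can be said to have none.
- A reader might infer that the trial gives up power outright. Holm cannot change the chance of at least one rejection, which is the goal in 10.1. If 10.4.1 governs, no alpha lapses; Holm would then lower power per hypothesis (86.9% to 84.6% in the 80% row) in return for restoring the familywise level.
- A reader might infer that the combined arm would end with no statement at all. Section 10.4.1 already reports its mean difference with an interval, which can be set against 1.5 mmHg. What is missing is a prespecified claim.
- A reader might infer that nested non-inferiority is free. It costs no type I error for multiplicity, but the margin is not stated for that arm. The As Treated population with baseline values imputed for failures and missing data may also pull differences towards zero and so favour non-inferiority.
- The statement in 10.4.4 that differences "will be evaluated using Dunnett's test" concerns exploratory endpoints and shows no inconsistency in the primary analysis.

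**Conclusion.** The point holds as a cheap improvement that also resolves a real conflict. Sections 10.1 and 10.4.1 give different levels for the same tests; the literal 10.4.1 rule has a familywise error of about 0.045 against the 0.025 implied by 10.1. Holm at 0.025 is never less powerful than the split. It adds about 4.6 points for each hypothesis and 9 for both, if each test has 80% power at 0.0125 with correlation 0.5. It adds nothing to the either/or goal.

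The sizes rest on assumed power, SD and effects. The recommendation is conditional on the redacted part of 10.1 not already giving a testing order. The combined-arm non-inferiority test is the sponsor's choice.

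**What to change.** 1. Correct the direction of Hypothesis II in 10.1, as any recycled test would inherit the error.
2. In 10.1 and 10.4.1, state one rule: Hypotheses I and II are tested by Holm at familywise one-sided 0.025. The smaller p-value is compared with 0.0125; if it is rejected, the other is compared with 0.025. State that this overrides the general default in 10.4.
3. Report two-sided 97.5% intervals beside the decisions.
4. Optional, if the sponsor justifies 1.5 mmHg for the combined arm: test its non-inferiority at one-sided 0.0125, or at 0.025 once Hypothesis II is rejected at 0.0125, whether or not Holm goes on to test Hypothesis I. Pass the combined arm's alpha to Hypothesis II only after superiority is shown, not after non-inferiority alone.

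Steps 1 to 3 need wording only, with no added patients, visits or data. Step 4 also needs a margin rationale. The cost is less simple intervals: a hypothesis rejected at Holm's second step can have a 97.5% interval that still reaches its null value, and the SAP should say so. Make the change before any outcome is seen by arm, including the descriptive interim analysis allowed in 10.6.

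### Hypothesis II is written in the wrong direction: with negative change meaning improvement, the non-inferiority test as stated succeeds when OMNI viscoelastic-only is worse than the comparator

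*Combined protocol and SAP*

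**What the plan says.** Section 10.1 (Sample Size Calculation) names two primary hypotheses on the change in unmedicated DIOP at 12 months. Hypothesis I is superiority of OMNI viscoelastic delivery plus trabeculotomy. Hypothesis II is non-inferiority of OMNI viscoelastic delivery alone, "with a non-inferiority margin of 1.5 mmHg".

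The sign convention is given twice. Under Hypothesis I in Section 10.1: "A negative mean change represents a mean reduction". In Section 10.4.1: "change = (12-month unmedicated DIOP – Baseline unmedicated DIOP".

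Hypothesis II is then written as "H_0: \mu_{01} - \mu_i \leq -1.5 \text{ mmHg}$ versus $H_a: \mu_{01} - \mu_i > -1.5 \text{ mmHg". In plain notation this is H0: μ01 − μi ≤ −1.5 versus Ha: μ01 − μi > −1.5, where μ01 is the mean change on OMNI viscoelastic-only and μi the mean change on the comparator. The same Ha appears a second time, in a sentence that cites the sign convention as its reason (negative means "represent decreases in IOP, the alternative hypothesis" and so on). That sentence gives the aim as to "prove that the mean change in unmedicated DIOP of the OMNI (ab-interno transluminal viscoelastic delivery alone) group is not worse than that of the" comparator by 1.5 mmHg.

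Section 10.4.1 applies a two-sample t-test "for Hypotheses I and II described in Section" 10.1. It does not restate the direction, and it gives no confidence-limit criterion for non-inferiority.

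**The concern.** A smaller pressure reduction on OMNI makes μ01 less negative than μi, so the difference μ01 − μi becomes positive. The inferior region that a non-inferiority test has to exclude is therefore μ01 − μi ≥ +1.5. The plan places H0 at the other end, where OMNI is better by 1.5 mmHg or more. Rejecting that H0 excludes a large OMNI advantage and leaves every degree of OMNI disadvantage open.

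The formula and the sentence that explains it cannot both hold. At stake is the decision rule for one of the two primary hypotheses. Followed literally, it grants the claim more readily the worse OMNI performs, and withholds it if OMNI is clearly better.

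**Working it through.** **1. Does the rest of the plan use the same convention?**

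| Place | Direction used |
|---|---|
| 10.1, Hypothesis I | Ha: μ02 < μi; success means the OMNI change "group is lower than that of the iStent inject group"; lower is better |
| 10.4.1, definition of change | 12-month minus baseline; lower is better |
| 10.4.2, tipping point | adding 0.05 mmHg to the OMNI value is called worse; lower is better |
| 10.1, Hypothesis II, formula (twice) | OMNI is protected only against being too low; higher counts as success |
| 10.1, Hypothesis II, prose | OMNI not worse by 1.5 mmHg; lower is better |

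The formula would be right if the difference were comparator minus OMNI, or if change were recorded as a positive reduction. Sections 10.1 and 10.4.1 exclude both. Only the Hypothesis II formula is out of line.

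**2. Inputs for the size of the effect.**
- Margin: 1.5 mmHg (Section 10.1).
- Sample size: 411 completers at 1:1:1 (Synopsis), so 411/3 = 137 per arm. Check against the plan's own total: 137/0.9 = 152.2, rounded up to 153; 3 × 153 = 459, the stated number to be randomized.
- Level: one-sided 0.0125, half of the two-sided 0.025 per hypothesis in Section 10.1, so z = 2.241. Section 10.4.1 gives one-sided 0.025 (z = 1.960) instead, so that was run as well.
- SD of change: not visible in the public document. SD 4 mmHg is an assumption, with a range of 3 to 6.

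**3. Formulas** (normal approximation). Let d be the true value of μ01 − μi, so positive d means OMNI is worse, and let SE = SD × √(2/137). For SD 4, SE = 4 × √(2/137) = 0.483.
- As written: P(claim) = 1 − Φ(z − (d + 1.5)/SE)
- Correctly directed: P(claim) = Φ(−z − (d − 1.5)/SE)

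**4. Results at SD 4, one-sided 0.0125.**

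| True d (mmHg) | As written | Correct direction |
|---|---|---|
| −3 (OMNI better) | about 0% | about 100% |
| −1.5 (OMNI better) | 1.25% | about 100% |
| 0 | 80.6% | 80.6% |
| +1.5 (OMNI worse by the margin) | about 100% | 1.25% |
| +3 (OMNI worse) | about 100% | about 0% |

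Example at d = +1.5, as written: (1.5 + 1.5)/0.483 = 6.21; 2.241 − 6.21 = −3.97; 1 − Φ(−3.97) is about 1.

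On the observed scale, the written rule succeeds when the estimated difference exceeds −1.5 + 2.241 × 0.483 = −0.42 mmHg. The correct rule needs it below +0.42 mmHg.

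**5. Range at d = +1.5.** For SD 3, 4, 5 and 6 at one-sided 0.0125, the written test claims non-inferiority about 100%, about 100%, 99.7% and 97.1% of the time; the correct test does so 1.25% of the time throughout. At one-sided 0.025 the written test gives 98.5% to 100% over the same SDs, against 2.5%.

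**6. Interaction with other parts of the plan.** Section 10.4.1 imputes baseline, that is a change of zero, for failures and missing values. An excess of such eyes on OMNI raises μ01 − μi and moves the result towards the written Ha. In Section 10.4.2, worsening the OMNI values and improving the comparator values also raises the difference, so the tipping-point shifts move the mean difference further into the written Ha and do not stress the claim.

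**The case against.** The strongest reply is that the intent is not in doubt. Section 10.1 states non-inferiority in words in the goal sentence and twice under Hypothesis II. Section 10.4.1 points to that whole section, words as well as symbols, and also calls for a two-sided 95% confidence interval for the mean difference, so a reader could compare its upper limit with +1.5. A wrong claim is therefore possible but not inevitable. That is fair, and the consequences above apply to the test as written. It does not remove the error: the inequality is printed twice, it is the only formal statement of the test, and an analyst who used the right direction would be departing from the stated hypothesis, which Section 10.7 requires to be noted in the final report.

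Three smaller points also stand:
- The percentages depend on an assumed SD. Agreement of the two tests at d = 0 holds for any SD, but the common value runs from 97.1% at SD 3 to 43.2% at SD 6 (one-sided 0.0125).
- The figure of 137 per arm is the completer count. Because missing 12-month values are imputed, up to about 153 per arm could be analysed. A larger n lowers the SE and makes the written test's false-claim rate at the margin slightly higher.
- Whether the sample size is untouched depends on the planned true difference, which is not visible. If it was zero, the two directions have equal power and the error would not have shown in the calculation. If it was not zero, they differ.

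**Conclusion.** The concern holds. The formal Hypothesis II contradicts its own explanation, the sign convention in Sections 10.1 and 10.4.1, Hypothesis I, and the direction used in Section 10.4.2. That conclusion needs no assumed figure.

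Applied literally, the test would declare non-inferiority for an OMNI viscoelastic-only arm that is worse by the full 1.5 mmHg margin in 97.1% to 100% of trials, where 1.25% is intended, and would almost always deny it to an arm that is 3 mmHg better. These figures assume 137 eyes per arm, an SD of 3 to 6 mmHg and a normal approximation. Because this is a primary decision rule, it must be corrected before the analysis.

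**What to change.** - **Section 10.1:** restate Hypothesis II as H0: μ01 − μi ≥ +1.5 mmHg versus Ha: μ01 − μi < +1.5 mmHg. The sign of the margin and the inequality both change in three expressions: H0, Ha, and the repeated Ha in the explanatory sentence.
- **Section 10.4.1:** add a sentence that non-inferiority is concluded only if the upper limit of the confidence interval for μ01 − μi, at the multiplicity-adjusted level, is below +1.5 mmHg. The differing levels in Sections 10.1 and 10.4.1 are a separate matter, but they must be reconciled for this sentence to be definite.
- **Section 10.4.2:** the shifts already run the right way. State that the Hypothesis II p-values come from the corrected test.

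The cost is a few symbols and two sentences, with no new data. The sample size is unchanged if it was planned at a true difference of zero; the sponsor should confirm that against the planning assumptions.
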